13.2 Procedures for Recording and Reporting Adverse Events

Adverse Event (AE): Any untoward medical occurrence in a subject to whom a therapy has been administered including occurrences which are not necessarily caused by or related to that therapy.

Adverse Reaction (AR): Any untoward and unintended response in a subject to a therapy which is related to any duration of therapy administered to that subject.

Unexpected Adverse Reaction (UAR): An adverse reaction the nature and severity of which is not consistent with the information known about the therapy in question in the view of the investigator

Serious adverse Event (SAE), Serious Adverse Reaction (SAR) or Unexpected Serious Adverse Reaction (USAR): Any adverse event, adverse reaction or unexpected adverse reaction, respectively, that

- Results in death;
- Is life-threatening;
- Required hospitalisation or prolongation of existing hospitalisation;
- Results in persistent or significant disability or incapacity;
- Consists of a congenital anomaly or birth defect.

Reporting Responsibilities

All SARs and SUSARs (excepting those specified in this protocol as not requiring reporting) will be reported immediately by the Chief Investigator to the R&D office

13.2.1 Adverse events that do not require reporting

No potential related adverse events are expected in this pilot trial. As part of the study interventions, the woman will access information on depression and antidepressant use in pregnancy. This will be done in the context of a health professional having recommended an antidepressant in pregnancy, so any queries or concerns arising from accessing this information via the study intervention would be addressed in the course of usual clinical care. If there are any concerns about a woman's mental health or risk during the course of the study (e.g. emotional distress, suicidal ideas), the researcher will alert the CI ([name]) and will arrange for the woman to have increased support from her clinical team.

13.3 Stopping Rules

The trial may be prematurely discontinued by the Sponsor or Chief Investigator on the basis of new safety information or for other reasons given by the regulatory authority or ethics committee concerned (for example if important new risk information emerges about antidepressant use in pregnancy during the study period which is not incorporated into the PDA).

The trial may also be prematurely discontinued due to lack of recruitment. If the study is prematurely discontinued, active participants will be informed and no further participant data will be collected.

The electronic version of this document is the latest version. It is responsibility of the individual to ensure that any paper material is the current version. Printed material is uncontrolled documentation.

14. Statistics

14.1 Sample Size

We estimated that a minimum sample size of 40 (20 per intervention arm) was required for this pilot RCT based on (a) a review by Hertzog, which suggested a range of 20-40 participants for assessing the acceptability of an intervention²³; and (b) pilot data for the primary outcome that we intend to use in a future efficacy RCT- the Decisional Conflict Scale (DCS). Among women with mean DCS score=30 (moderate-high) and SD 14.8 (based on pilot data), a total sample size of 40 participants would allow the detection of a 13-point difference in DCS scores (clinically significant) between intervention & control groups with probability (power) 0.8 (alpha=0.05). We aim is to recruit at least 25 participants to each intervention group, allowing for 20% loss to follow-up for a minimum of 20 per group retained in the study.

In the hospitals affiliated with King's Health Partners (King's College Hospital and Guy's and St Thomas's Hospitals) there are approximately 12,000 deliveries per year. Based on UK national data and Toronto pilot work, we assume that (a) at least 3% of pregnant women would be considered for an antidepressant (based on national UK data),²⁴ and (b) 40% of these women would be eligible for this study,¹⁰ and (c) 60% of those eligible would agree to participate¹⁰. Therefore, if all potentially eligible women were identified and referred to the study team, we could reach our recruitment target of 50 women over a 7-month period in our study setting. In practice, we have discovered that the rate of identification and referral of potentially eligible women into the study is extremely low (over a 5-month period seven potentially eligible women were referred to the study, of whom two were eligible and one participated in the study). We are therefore expanding to include national recruitment via online advertising and information sent to relevant clinicians.

14.2 Randomisation

Participants will be randomized 1:1 ratio with stratification by whether they are currently pregnant or planning pregnancy.

Researchers will be blind to group allocation at all data collection time points. PDA acceptability data will be collected by a different researcher in order to maintain blinding. Participants cannot be blinded as to which intervention they received, due to the nature of the intervention, but they will be blinded to study hypotheses. Providers may or may not become aware of the participant's allocation depending on whether or not participants discuss their use of the PDA with them. However, providers will not collect outcome data, minimizing risk for measurement bias due to lack of blinding.

14.3 Analysis

(1) *Statistical analysis:* Means will be calculated to determine feasibility and compliance estimates for recruitment rate for each strategy, rates of nonparticipation, completion rate of the PDA, follow-up rates at the various intervals, and so on. We will calculate the acceptability of the intervention using the Likert-type scale responses from the participant and provider questionnaires, and will collate additional comments made by participants or providers for consideration of modifications to

The electronic version of this document is the latest version. It is responsibility of the individual to ensure that any paper material is the current version. Printed material is uncontrolled documentation.

the content, layout or technical capacity of the PDA. To compare decisional conflict between women receiving the PDA to women receiving the comparison condition at 4 week follow-up we will use the intention-to-treat principle. Missing data points will be excluded from the analysis, and individuals with less than 2 DCS measurements will be treated as lost to follow-up. An on-treatment analysis will also be performed as a sensitivity analysis (for best possible performance of the PDA). Means of the DCS scores of the experimental and comparison groups at the primary endpoint will be compared using a one-way ANCOVA model, where the covariate will be baseline DCS score. Results will be stratified by centre. This effect size will be used to generate the sample size needed for the future RCT

(2) *Qualitative analysis*: after transcribing the audiotaped follow-up appointment, data will be analysed using framework analysis (which entails the 5 key steps of familiarisation, coding, developing an analytical framework, indexing and data interpretation).⁶ The interview will also be analysed using the observer-rated OPTION Scale for shared decision-making.⁵

15. Trial Steering Committee

A Trial Steering Committee will not be used for this small, low-risk pilot RCT.

16. Data Monitoring Committee

Because of the low risk nature of this intervention, an independent Data Safety Monitoring Board will not be developed. Safety will be assessed at all follow-up time points and be routinely reviewed by the PI. Adverse events will be recorded and serious adverse events immediately reported (within 24 hours by telephone or fax) to the CI ([name]) for consideration of further action.

17. Direct Access to Source Data and Documents

The Investigator(s) will permit trial-related monitoring, audits and REC review by providing the Sponsor(s), and REC direct access to source data and other documents (eg patients' case sheets).

18. Ethics & Regulatory Approvals

The trial will be conducted in compliance with the principles of the Declaration of Helsinki (1996), the principles of GCP and in accordance with all applicable regulatory requirements including but not limited to the Research Governance Framework and the Mental Capacity Act 2005.

This protocol and related documents will be submitted for review to London - Queen Square Research Ethics Committee (REC)

The Chief Investigator will submit a final report at conclusion of the trial to the funder, the REC and the Sponsor

19. Quality Assurance

Monitoring of this trial will be to ensure compliance with Good Clinical Practice and scientific integrity will be managed by the study team. A committee consisting of the UK and Canadian PIs and study co-investigators and the research assistants will hold teleconferences as necessary (every 2 months) to discuss study progress, including participant recruitment, and unexpected issues. The lead sponsor, King's College London, will take primary responsibility for ensuring that the design of the trial meets appropriate standards and that arrangements are in place to ensure appropriate conduct and reporting.

The electronic version of this document is the latest version. It is responsibility of the individual to ensure that any paper material is the current version. Printed material is uncontrolled documentation.

20. Data Handling

The Chief Investigator will act as custodian for the trial data. The following guidelines will be strictly adhered to:

- Patient data will be anonymised
- All anonymised data will be stored on a password protected computer.
- All trial data will be stored in line with the Data Protection Act.
- and archived in line with Sponsor requirements

21. Data Management

Two electronic databases will be created using Excel spreadsheets (a) a database with identifying data (name, contact details), which will be password-protected and (b) a separate anonymised database, using study IDs only, which will contain study-specific outcomes (e.g. details on eligibility, consent, reasons for non-participation and findings from the baseline and follow-up assessments). Data will be handled in line with the Data Protection Act as detailed in section 20.

22. Publication Policy

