To address this gap, we have developed an electronic PDA for antidepressant use in pregnancy. The PDA was developed by leading international experts in Canada, with expertise in decision aids, perinatal psychiatry and psychopharmacology ([name], PI, was on the advisory group and [name], co-investigator, led the development). The PDA's content and layout were informed by: (1) The International Patient Decision Aids Standard (IPDAS) collaboration guidelines¹³; (2) Published systematic reviews of evidence related to the benefits and harms of antidepressant treatment in pregnancy (several conducted by team members)¹⁴⁻¹⁷; and (3) Evidence related to the decisional needs of patients faced with this complex decision.^{10,11} The prototype was developed by the healthcare technology company, QoC Health (<http://qochealth.com/>). It was revised on the basis of feedback from a multidisciplinary international steering committee, and the findings of an open-label acceptability trial in the target population. The PDA's content and format are described in section 8.1 below (see Appendix for further details).

The proposed study is a pilot RCT of this PDA based in London with nationwide recruitment, to be conducted in parallel with a pilot RCT in Toronto. The latter is already underway, following an open-label trial (N=13 patients); which found that the PDA was acceptable to patients and that its use was associated with a 52% reduction in the Decisional Conflict Scale score. The findings from the pilot RCTs in London and Toronto will inform a future international definitive RCT.

7. Trial Objectives and Design

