7.1 Trial Objectives

The **primary objective** of this pilot study is the feasibility of conducting a large RCT to evaluate the efficacy of the PDA. This comprises 1) feasibility (how well the trial protocol can be implemented), (2) acceptability (usability and tolerability of the intervention and of randomisation including patient and provider views) and (3) adherence (the degree to which the trial protocol is followed). **Secondary outcomes** will include preliminary effect sizes of the PDA to inform sample size calculations for the future RCT.

Primary endpoints

(A) Feasibility: Measured in terms of (1) eligibility (e.g. proportion of patients eligible); (2) recruitment (e.g. rates overall and by recruitment strategy, non-participation reasons); and (3) timing (e.g. enrolment to first log-in to the PDA).

(B) Acceptability: This will measured by: (1) The Decision Support Tool Acceptability Questionnaire (for participants randomized to receive the PDA intervention only). (2) Study website usage (including number of women who complete the PDA; number of electronic logins & length of time required to complete the PDA; number of participants who use the PDA summary sheet with their provider); (3) The Provider Perspective Survey

(C) Adherence with trial protocol: This will be measured by: (1) number of participants who follow-up with their clinician within the intended active study phase (i.e. 4 weeks post-randomization); and (2) The rate of follow-up data collection at each time point.

Secondary endpoints

Secondary outcomes will inform the sample size required for a future RCT of the effectiveness of the tool. Decisional conflict will be the primary outcome for the future RCT, as has been the case in previous PDA studies,^{18,19} measured using the Decisional Conflict Scale.²⁰ Secondary outcomes measures for the future RCT are listed below.

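### Section 14.3 sizes the future RCT from the pilot's observed ANCOVA effect on decisional conflict; with 20 per arm and a baseline correlation of 0.5, that gives anywhere from about 6 to 104 per arm when 16 are needed

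*Combined protocol and SAP*

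**What the plan says.** Section 14.3 compares mean DCS at 4 weeks by a "one-way ANCOVA model, where the covariate will be baseline DCS score". It adds "Results will be stratified by centre" and then "This effect size will be used to generate the sample size needed for the future RCT".

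Two other places point the same way. The secondary objective in the synopsis says that efficacy estimates from the pilot will inform the later sample size, and section 7.1 says that secondary outcomes "will include preliminary effect sizes of the PDA to inform sample size calculations for the future RCT". Section 12.2 repeats the purpose. Section 6 brings in the parallel Toronto pilot: "The findings from the pilot RCTs in London and Toronto will inform a future international definitive RCT".

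Section 14.1 gives the only SD, 14.8 from pilot data, and says that 40 women "would allow the detection of a 13-point difference in DCS scores (clinically significant) between intervention & control groups" with power 0.8 at alpha 0.05. It plans 25 recruited per arm so that at least 20 remain after 20% loss.

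The documents give no target difference for the future trial and no allowance for the imprecision of the estimated effect. They do not say which SD goes with that effect, give no correlation between baseline and 4-week DCS, and give neither Toronto's sample size nor a method for combining the two pilots.

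**The concern.** The number per arm depends on the squared ratio of SD to effect. A pilot of 20 per arm estimates the SD fairly well and the effect poorly. If the observed effect is entered directly, a pilot that by chance sees a large effect yields an undersized definitive trial, and one that sees a small effect yields an inflated trial.

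Informing the later sample size is the pilot's stated secondary objective, so the way it is done deserves a defensible rule. The 13 points in section 14.1 are called clinically significant, but no source is given, they are presented as what 40 women could detect, and section 14.3 does not tie the future trial to them.

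**Working it through.** **Inputs from the documents.** SD 14.8, difference 13, power 0.8, alpha 0.05, and 25 recruited and 20 retained per arm (section 14.1); ANCOVA on baseline DCS (section 14.3).

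**Assumptions.**
- 14.8 applies at 4 weeks (section 14.1 does not say so).
- The true effect is 13.
- The future trial uses two-sided 5% and 80% power.
- Baseline to 4-week correlation r is 0, 0.5 or 0.7.
- The future trial is sized on the residual SD.
- Toronto brings the pilot to 40 per arm in the last scenario.

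**The plan's own figure.** n per arm = 2(1.96 + 0.842)² (SD/effect)² = 15.70 × (14.8/13)² = 20.3, so 21. With 20 per arm, power is 0.793 by normal approximation (0.772 by t-test). Section 14.1's 40 therefore reproduces closely, and 20/(1 − 0.20) = 25 per arm also checks.

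**Precision of the pilot effect, 20 per arm.** Residual SD = 14.8√(1 − r²); SE = residual SD × √(2/20); half-width = t(0.975, 37 df) × SE.
- r = 0: SE 4.68, half-width 9.5 points.
- r = 0.5: SE 4.05, half-width 8.2 points.
- r = 0.7: SE 3.34, half-width 6.8 points.

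**One case by hand, r = 0.5.** Residual SD is 12.82. The need is 15.70 × (12.82/13)² = 15.3, so 16. The observed effect has a 95% range of 13 ± 1.96 × 4.05, that is 5.06 to 20.94. Entering these limits gives 15.70 × (12.82/5.06)² ≈ 101 and 15.70 × (12.82/20.94)² ≈ 6. Letting the SD vary too gives 6 to 104.

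**All cases.** Each setting uses 1,000,000 simulated pilots. The effect is drawn from N(13, SE) and the residual SD from a chi-square with 2m − 3 degrees of freedom, where m is the number analysed per arm. Both go into the formula, rounded up. The future trial's power is then computed at the true effect and true residual SD. Power shares are among pilots with a positive effect; non-positive effects are under 0.3% here.

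| Pilot, per arm | r | Need | 95% range of n | Middle 50% | Power below 60% |
|---|---|---|---|---|---|
| 20 | 0.5 | 16 | 6 to 104 | 10 to 25 | 20% |
| 20 | 0.7 | 11 | 4 to 44 | 8 to 16 | 15% |
| 20 | 0 | 21 | 7 to about 240 | 13 to 36 | 23% |
| 25 (no loss) | 0.5 | 16 | 6 to 76 | – | 17% |
| 25 (no loss) | 0.7 | 11 | 5 to 36 | – | 12% |
| 25 (no loss) | 0 | 21 | 7 to 152 | – | 20% |
| 40 (assumed, with Toronto) | 0.5 | 16 | 7 to 49 | – | 11% |
| 40 (assumed, with Toronto) | 0.7 | 11 | 6 to 26 | – | 7% |
| 40 (assumed, with Toronto) | 0 | 21 | 9 to 84 | – | 14% |

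At 20 per arm the low end is about 3 times too small (16/6 = 2.7, 11/4 = 2.8, 21/7 = 3). The high end is 44/11 = 4, 104/16 = 6.5 and 240/21 ≈ 11 times too large.

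**If the unadjusted SD were used instead.** At r = 0.5 and 20 per arm, n runs from 7 to 137. Power below 60% falls to 8%, but n is at least twice the need in 27% of pilots.

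**The alternative rule.** Use a fixed 13-point target and the one-sided upper 80% confidence limit of the SD, with 20 per arm. If the truth is 13, n runs from 12 to 29 (r = 0.5), 8 to 20 (r = 0.7) and 16 to 39 (r = 0), and power is below 60% in at most 0.5% of pilots. If the truth is 6.5, about 98% of the resulting trials have power below 50%, against 22% to 30% under the current rule (among pilots with a positive effect).

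**The case against.** The best defence is that one sentence in a short pilot analysis section is being read as a mechanical rule. The documents describe a large, international, definitive trial informed by two pilots, and they call the estimates potential or preliminary. A definitive trial of 6 per arm would not fit that description, and the later trial will need its own justification. This limits the weight of the point. It does not remove it, because the sentence names only the observed effect as the input.

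The defence also rightly rules out several stronger readings:

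- *Leading with 7 to about 240.* That is the r = 0 case. The plan specifies ANCOVA, so it is the wide end; any useful correlation narrows it. All these are also 95% ranges, and roughly two thirds to four fifths of pilots at 20 per arm land between half and twice the need.
- *A trial many times too small.* At the 2.5th percentile the shortfall is about threefold at most. The larger multiples are all on the oversized side.
- *Section 14.3 as the only text that names the input.* The synopsis and section 7.1 also name efficacy estimates or effect sizes.
- *A defect in the pilot itself.* Recruitment, conduct, the DCS comparison and the feasibility objective do not depend on the sentence.

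Finally, the alternative is a trade-off. It protects power only at the chosen target, and it does worse than the current rule if the target is set well above the truth. That objection stands and shapes the fix.

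**Conclusion.** The point holds as a minor one. Taken as written, the rule makes the future sample size unstable: by chance it can give a trial up to about 3 times too small or, across r = 0.7 to 0, about 4 to 11 times too large. Future power falls below 60% in 15% to 23% of pilots with 20 per arm, and in 7% to 14% with an assumed 40 per arm. Better baseline correlation or Toronto data reduce the instability without removing it: even at r = 0.7 the range with 20 per arm spans about elevenfold (4 to 44).

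The figures rest on the assumptions listed with the calculation. The correlation and Toronto's size are not in the documents, so the ranges should be read as a span and not as one estimate.

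**What to change.** Replace the sentence in section 14.3 with:

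> The future RCT will be sized on a pre-specified, justified smallest important DCS difference, fixed before the pilot effect is known. The pilot (with Toronto data where available, and the method of combining the two stated) will supply the 4-week SD, with an allowance for its imprecision such as its one-sided upper 80% confidence limit, the baseline to 4-week correlation, and attrition. The SD used will match the planned analysis. The observed difference will be reported with its 95% CI and used only to check that the target is plausible.

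Bring the synopsis and section 7.1 into line.

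The cost is wording in three places and one team decision on the target; no new data are needed. The future trial may be somewhat larger because the SD limit is conservative: at r = 0 with a 13-point target, the median is 25 per arm against a need of 21. A smaller target costs more, with medians of about 43 per arm for 10 points and about 100 for 6.5. Thirteen points should be the target only if the team confirms that smaller differences are not worth detecting.
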